Exempt research still requires review by the Human Research Protection Program. Choose this option if you believe your study is:

- Research in a common educational setting (e.g. school, daycare) about normal educational practices.
- Educational Test, Survey, Interview, or Observation of Public Behavior
- A benign intervention involving short puzzles, games and their outcomes on human behavior conducted during a single day.
- Secondary Analysis of data, documents, records, pathological or diagnostic specimens that are publicly available or properly deidentified.
- Taste and Food Quality Evaluation or Consumer Acceptance Studies.

Non-exempt study

✓ *Research that does not fit into an exempt category typically involves the collection of new data from a participant.*

Just-in-time

I have been contacted by a sponsor (often NSF or NIFA/USDA) to provide documentation of IRB approval, (such as Just-in-Time or JIT) but my application to the IRB is dependent on other factors such as:

- *completion of instruments*
- *prior animal studies*
- *purification of compounds*

Note: This category should be utilized ONLY if the above criteria apply. If study procedures are discernible at the time of the sponsor request, please do not select this option. The research team should affirm that their sponsor will accept documentation for a development protocol.

If you request this study type, the title of the IRB protocol must exactly match the title of the grant proposal. Most funding agencies will not accept protocols with different titles.

Quality Improvement

My research involves activities without a plan to conduct research (Case Report or Quality Improvement project)

I need to know if my project is considered "Human Subjects Research"

I would like to request that another IRB Review this study. (Request for Purdue IRB to defer to another site).

When Purdue University will be engaged in human subject research with one or more institutions, investigators may submit a Request for Deferral asking that the review be deferred to one institution's Institutional Review Board (IRB).

Research Classification and Special Considerations

Would you determine that this research is predominately social or biomedical in nature

When you provide an answer to this question, a series of additional questions will display, and checking on each of these questions will generate a new form to the left that you will need to complete. These forms will ask the questions we used to ask, but in a clearer and more organized way, which will help the reviewer, as well as the investigator.

Biomedical

My research has a biomedical focus.

Social / Behavioral

My research has a social or behavioral focus.

A combination of social science and biomedical, or I'm not sure.

*required

Please check any of the following that apply to the proposed research.

Each of these involves special considerations in the IRB review. If none of these items apply, click on "None of These" and continue forward in the application.

Potentially Vulnerable Populations

Examples: Children, Pregnant Women/Fetuses, Prisoners, those that lack capacity to consent), economically disadvantaged persons, minorities.

Use of an Experimental Drug

A substance manufactured via chemical process and intended for use in the diagnosis, cure, mitigation, than food) intended to affect the structure or any function of the body of man.

Note: Studies of this nature are considered Applicable Clinical Trials and may require an Investigational and Drug Administration and involvement of a physician investigator.

<https://www.fda.gov/vaccines-blood-biologics/development-approval-process-cber/investigational-new-c>

Use of an Investigational Medical Device

An instrument, apparatus, implement, machine, contrivance, implant, in vitro reagent, or other similar or

or accessory, which is intended for use in the diagnosis of disease or other conditions, or in the cure, m in man or other animals, OR intended to affect the structure or any function of the body of man or other primary intended purposes through chemical action within or on the body of man or other animals and v metabolized for the achievement of its primary intended purposes.

Note: Studies of this nature are considered Applicable Clinical Trials and may require an Investigationa Drug Administration and involvement of a physician investigator.

<https://www.fda.gov/vaccines-blood-biologics/development-approval-process-cber/investigational-new-c>

Clinical Trial

PLEASE READ THIS DEFINITION CLOSELY.

NIH defines a Clinical Trial as "A research study in which one or more human subjects are prospectively assigned to one or more interventions (which may include placebo or other control)

- ✓ *to evaluate the effects of those interventions on health-related biomedical or behavioral outcomes."*

If this determination applies, please check this box.

Research with Food

Articles used for food or drink (or for components of such articles) and NOT intended for use in the diagnosis, cure, mitigation, treatment, or prevention of disease.

Radiation and/or Imaging

X-ray, CT, PET scans, nuclear medicine procedures, and MRI scans.

This protocol requires for research purposes 1) radiological assessments and procedures that involve radiation exposure (X-ray, CT, PET scans) 2) nuclear medicine procedures (imaging or therapeutic) or 3) MRI scans.

Nursing or Study Physician Resources

This protocol will have Nursing or Study Physician Resources

Blood Collection for Research Purposes

This protocol involves collection of blood samples other than discarded specimens. Examples are collections involving finger stick, venipuncture, or indwelling catheters.

Human Biological Specimen Repository

This protocol involves the establishment of a biological specimen repository.

Repositories are used for prospective collections of specimens that are processed, stored and

distributed to multiple investigators for use in research.

Gene Research Classification

The study will collect samples from individuals and look at a single gene, group of genes, or full genome for the purposes of research.

Stem Cells

This protocol includes an intervention with human subjects that involves either

- a) the derivation of stem cells,*
- b) the implantation of stem cells.*

International Research

This protocol includes research that is conducted at a non US location.

Data Controlled Under HIPAA and/or FERPA

Health Insurance Portability and Accountability Act (HIPAA) covers individually identifiable health information held or transmitted by a covered entity. This often involves healthcare providers and insurance companies.

AND/OR

Family Educational Rights and Privacy Act (FERPA) protects the privacy of student education records.

Biological Product

A substance manufactured via biological process and otherwise meets the above definition of a drug; includes a wide range of products such as vaccines, blood and blood components, allergenics, somatic cells, gene therapy, tissues, and recombinant therapeutic proteins.

Dietary Supplement

A product taken by mouth that is intended to supplement the diet and that contains one or more dietary ingredients.

Community-engaged research

This is community-engaged research. For the purposes of IRB at Purdue University, community-engaged research is defined as research that includes the meaningful involvement of community partners in the research process, including but not limited to topic development, need identification, research design, conduct of research, and/or sharing of results.

Incidental Findings

Incidental findings are discoveries of individual-level findings that are unrelated to the goals of the study. (e.g. genetic data, MRI or test results).

Deception or incomplete disclosure

Deception occurs when an investigator intentionally gives research participants misleading or false information about some aspect of the research.

Incomplete Disclosure occurs when an investigator intentionally withholds information from participants about the true purpose or nature of the research.

None of the above apply.

Protocol Description

Helpful links and relevant guidance can be found by clicking the question mark in the top-right corner of each question.

*required

Tell the IRB what specific trait(s), function(s) or behavior(s) you would like to study. Give a brief summary of your study in simple terms.

Describe why you are conducting the study. Identify the research question(s).

More than 50% of U.S. adults have elevated blood pressure or hypertension which increases the risk of cardiovascular disease (CVD). Early detection of elevated blood pressure or stage 1 hypertension offers a window of opportunity to prevent progression to overt hypertension and CVD through behavioral modification. Sympathetic activation and arterial stiffness are both deleterious factors that concomitantly contribute to elevated blood pressure. Mindfulness-Based Stress Reduction (MBSR) programs have been shown to reduce blood pressure in adults, but the mechanisms for the reduction remain speculative.

*required

Specific Aims/Objectives

Give the IRB an example of potential discoveries you hope to make or insight you hope to share. For example, outline a disease state, social characteristic or behavior that might benefit from the study results.

We will systematically examine 24-hour blood pressure regulation and two potential mechanisms for the anti- hypertensive effects of MBSR by directly assessing muscle sympathetic nerve activity (MSNA) and arterial stiffness. Aim 1 will determine if MBSR improves 24-hour blood pressure regulation, aim 2 will determine if MBSR reduces sympathetic neural activity, and aim 3 will determine if MBSR will decrease arterial stiffness in prehypertensive adults. This project will also provide advanced research opportunities to undergraduate and graduate students in health-related fields at Purdue University Northwest, consistent with the goals of the Academic Research Enhancement Award (R15) mission.

*required

Background and Significance

Include how previous research studies and their results support your study or how you will build upon existing information.

The proposed research is relevant to public health because over 50% of adults in the U.S. have elevated blood pressure or hypertension. The project is relevant to NIH's mission because it will provide rigorous investigation on Mindfulness-Based Stress Reduction as a proactive anti-hypertensive lifestyle intervention that may improve blood pressure regulation through sympathetic nerve control and arterial stiffness.

*required

Research Hypotheses

Please list any relevant study hypothesis/hypotheses. If this does not apply, type "Not Applicable".

Our central hypothesis is that MBSR will: 1) improve nocturnal blood pressure dipping and / or reduce early-morning surges, 2) reduce resting MSNA and attenuate the neural cardiovascular responses to acute stress, and 3) decrease arterial stiffness. We will utilize a parallel, randomized, control design (MBSR vs. active control) that includes gold-standard techniques for measuring blood pressure (24-hour ambulatory assessment), MSNA (microneurography), and arterial stiffness (applanation tonometry).

*required

How long will participants be asked to be in the study?

List the approximate duration in the fashion below.

- *Number of Visits =*
- *Minutes or Hours per visit =*
- *Single Day or Multiple Days?*
- *Total number of months until all data are collected =*

Potential participants visit the laboratory on three non-consecutive days for screening visits that take approximately 15 minutes each. We have included 3 pre-screening blood pressures to ensure that participants meet the primary requirement for elevated blood pressure. This procedure was proposed in

the original NIH proposal, has been used throughout this study so far, and has been used in previous projects we had funded through the NIH.

Qualified participants visit the lab two more times, once before and once after the 8-week intervention (within 10 days of the start and finish). Each of those visits take about 3 hours. The mindfulness-based stress reduction (MBSR) and stress management education (SME) classes (interventions) meet once per week for 2 to 2.5 hours. There is also one Saturday requirement at the end of the 6th week for about 7-8 hours. At home daily practice for participants in the two classes ranges from 30-45 minutes. The entire study with pre- and post-testing is approximately 10 weeks.

We specifically set up these courses for the research study. However, eight week mindfulness-based stress reduction courses are offered around the world by qualified instructors. We plan to have one of our previous instructors ([name]) offer the course to the final cohort of participants in the spring of 2022. I will assist my graduate student [name] to offer the 8-week stress management education course. The SME course is traditionally used as an active control course for meditation studies, and to my knowledge it is not offered as an independent course like MBSR. Most of the MBSR and SME courses will be offered online via Zoom. There is one Saturday class for each of the interventions that we will try to hold in person on the Hammond campus.

*required

Specific Study Procedures

Describe in detail what a research participant will be asked to do.

- Prior to the start of the 8-week program, a 24-hour blood pressure reading will be taken. The device is compact and easily attached to a belt. Participants will also be fitted with a wrist accelerometer (similar to a Fitbit) that will track sleep-wake cycle for five consecutive nights. Participants will also complete questionnaires for anxiety, five-facets of mindfulness, and the ability to decenter.
- Following the accelerometer recordings, nervous system functions will be tested with microneurography (small electrode needle that can measure electrical activity in nerves) in a baseline setting along with a mental stress test (doing mental math calculations). Nerve activity will be continuously measured during the baseline and mental stress test. In addition to the nerve recordings, heart rate will be recorded with 3-lead electrocardiography, and continuous blood pressure with a small cuff on the middle finger. We will also estimate arterial stiffness with a small probe that will be placed at the radial (wrist), carotid (neck), and femoral (groin) pulse sites. We can also estimate breathing rate with an elastic pneumobelt that goes around the rib cage (fits gently outside of the participant's clothing). Breathing rate is not considered a primary variable, but we may report breathing rate (breaths per minute) if we calculate results for heart rate variability.
- With the programs outlined, participants will then proceed with the 8-week program to which they were randomly assigned. It is requested that you do not change your normal exercise schedule or eating habits. Both the MBSR and active stress management control programs will require a once

weekly group meeting and at home exercises. The home practice for MBSR participants includes things like breathing awareness, body scanning, and gentle Yoga. The home practice for SME participants includes daily reading from the book "Why Zebras Don't Get Ulcers" and gentle resistance band training. We have free copies of the required book that are lent out to participants during the 8-week class.

- Once the 8-week program is completed, participants will once more complete the questionnaires, 24- hour blood pressure readings, accelerometry, microneurography, heart rate, blood pressure, and arterial stiffness readings.
- Related to our laboratory safety, our new Tuttnauer 1730M autoclave is 20+ feet away from where participant testing would take place, and will never be used while a participant is in the laboratory. We have used this same autoclave for more than 15 years, and it has a very secure door latch. We have always worn neoprene gloves when prepping the electrodes to be autoclaved and when removing the electrodes from the autoclave in the sterilized pouches. We will use 3.5" x 10" self seal sterilization pouches made by PlastCare USA, that have an indicator strip that changes from blue to brown during the autoclaving process. We will follow additional PPE protocols during the COVID pandemic such as wearing a facemask during the autoclaving procedure.

In long term studies, a visual representation of a timeline is helpful. You may upload a visual representation as a Word (.docx) or PDF file [here](#).

[MBSR Conceptual Overview.pdf](#)

Attach any surveys, questionnaires, assessments

For purposes of recordkeeping, the HRPP/IRB will need to have a Word or PDF version of any Qualtrics or electronic survey questionnaires. Please include more than a link to the survey.

[MBSR Study Questionnaires.pdf](#)

[UFI_Pneumotrace_Datasheet.pdf](#)

[Actiwatch Spectrum PRO Brochure.pdf](#)

Flow charts, schemas

[MBSR Conceptual Overview.pdf](#)

References

Below are references that we cite in our complete IRB proposal:

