Study Protocol and Statistical Analysis Plan

Cover Page

[figure not shown]
NCT03626363

Mindfulness and Neural Cardiovascular Control in Humans

February 23, 2021 (Purdue IRB Approval Date)

Study Protocol

The figure below provides a conceptual overview of this R15 project. Our study assessed traditional cardiovascular disease risk factors such as blood pressure, but also focused on non-traditional risk factors such as muscle sympathetic nerve activity (MSNA) and arterial stiffness. In addition, we included key psychological assessments such as anxiety, perceived stress, and mindfulness. Finally, our neural cardiovascular assessments were completed at rest and during acute mental stress. We attempted to recruit 60 participants with elevated blood pressure to undergo an 8-week MBSR or active control protocol as outlined below to meet the proposed specific aims. We randomized qualified participants into the MBSR or active control. All autonomic and arterial stiffness measurements were completed at a similar time of day for pre-treatment assessments within one week before participants started the active control (i.e. stress management education) or MBSR interventions, and post-data was collected within one week after participants completed their intervention again at a similar time of day. Pre- and post-intervention ambulatory blood pressure monitor (ABPM) measurements started at a similar time on a work or school day.

Statistical Analysis Plan

The statistical approach for the research aims are outlined below. The power analyses were based on previous MBSR and MSNA-related work. A priori power analysis indicated that a sample size of 40 participants (20 per group) was needed to provide sufficient statistical power (~0.89) to detect a ~4 bursts/min in mean difference for resting MSNA using a mixed-effect analysis of variance model with repeated measures and an alpha of 0.05. We aimed to enroll a total of 60 individuals to ensure a minimum final sample size of 40 (MBSR = 20; active control = 20) with an estimated power of ~89%. We expected that some participants may not complete the 8-week protocol and we may occasionally have unsuccessful MSNA recordings. Thus, we aimed to recruit 30 participants for each group as outlined in Figure 1 and expected a minimum 67% retention rate to yield a final sample of at least 20 per group.

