If a larger number of subjects must be enrolled to account for such things as screening failures and drop-outs, provide an estimate of the larger number of subjects to be recruited through Purdue University. Please describe the rationale.

Consider:

- *Whether the withdrawal of the subjects might result from a decision by the subject or by the investigator, and the reasons for the withdrawal, if known; and*
- *Whether the withdrawal might occur from all components of the research study or just the primary interventional component.*

Based on our previous cohorts we have lost up to 20% of enrolled participants during the longitudinal study. We have set a target to complete 24 more participants through the longitudinal study, so enrolling 30 new participants should help us to meet that objective.

*required

Age(s) of Participants in Study Population

Please include an age range for subjects, if relevant. If the research has multiple subject groups, describe the requirements for each separately.

Newborn to less than 10 years old

10 years old and less than 18 years old

18 to 65 years old

Enter specific age range if the target population age is less than 65.

18 to 55 years old

65 years and older

Unknown- Data are deidentified of any age or date of birth

*required

Inclusion criteria - Please identify the population that you would like to study.

Your study should only include those who are able to participate and those who represent the population where your study is relevant. List the criteria that make someone eligible for your study.

Age between 18 and 55 years

Must have an average seated clinical blood pressure >120 mmHg systolic and / or >80 mmHg diastolic

Must have a body mass index < 30 kg / sq. m

Not be taking any cardiovascular medication

*required

Exclusion criteria - Please identify the characteristics that do not represent your intended study population.

Exclusion criteria are not simply the inverse of inclusion criteria. There might be individuals who should not participate in your study because it could be too risky or interfere with a condition. Please provide information about why the group will need to be excluded.

For NIH funded protocols: If you do not include women, minorities and children in your subject pool, you must include a justification for their exclusion. The justification must meet the exclusionary criteria established by the NIH.

Anyone with signs, symptoms, or diagnosis of COVID-19

Pregnant women

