Will the study provide (money/gift cards/inducements/discounts/entry into a drawing/course credit) in exchange for a person's participation in the study? Please note that Purdue University policies might affect how you can compensate subjects. Please contact your department's business office to ensure your compensation procedures are allowable by these policies.

Yes

*required

Describe the payment arrangement, including amount and timing of disbursement.

If the compensation includes a lottery or raffle-style drawing, please provide the approximate odds of winning (number of prizes, anticipated number of participants).

If course credit will be offered, please provide the amount and the percentage of the total grade. Extra credit should be no more than 3% of the course grade in order to avoid undue influence.

Participants will receive the following: 1) \$50 for each microneurography (autonomic) session completed; and 2) \$200 for the completion of the 8-week MBSR or SME course (prorated as \$25 per week completed if there is any need to withdraw before the completion of the 8-week course). The maximum payment that you can receive from this study is \$300. According to the rules of the Internal Revenue Service (IRS), payments that are made as a result of participation in a study may be considered taxable income. Participants will be asked to

provide their full name, address, and social security number for our Human Subject Invoice Log so that our Business Office at Purdue University Northwest can process and send a payment to the participant.

We did not have any budgeted funds through NIH for the screening visits, and have already screened 139 potential participants while at Michigan Tech that did not receive payment for screening. Thus, it would not be feasible or ethical to add payments for screening at this point.

*required

Justify the proposed payment arrangement described above, specifically why payment does not provide undue influence for subject participation

Explain how the amount is reasonable for the study.

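### The post-test is tied to completing the 8-week class, and no outcome visit is scheduled for randomised participants who stop the class but could still attend the laboratory

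*Combined protocol and SAP*

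**What the plan says.** The post-test appears in three places. Specific Study Procedures, identical in each copy of the IRB application, says "Once the 8-week program is completed, participants will once more complete the questionnaires" and lists the 24-hour blood pressure, accelerometry, microneurography and arterial stiffness measurements with it. The Study Protocol overview says that "post-data was collected within one week after participants completed their intervention". The application's section on study duration says that qualified participants attend "once before and once after the 8-week intervention (within 10 days of the start and finish".

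Early stopping is foreseen. The sample-size paragraph of the SAP states: "We expected that some participants may not complete the 8-week protocol and we may occasionally have unsuccessful MSNA recordings". For those reasons it enrols 60 and "expected a minimum 67% retention rate to yield a final sample of at least 20 per group". Attrition Considerations reports that "we have lost up to 20% of enrolled participants during the longitudinal study". The form asks there whether withdrawal might be from the whole study or only from the interventional component; the answer is a single figure that does not separate the two. Compensation for Research Participation prorates the class payment "if there is any need to withdraw before the completion of the 8-week course", and pays $50 separately for each microneurography session completed.

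The SAP analyses each aim by repeated measures ANOVA with two groups and two times. It gives no rule for participants without a post value.

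**The concern.** Stopping the class happens after randomisation and may depend on the arm. Both classes ask for 30 to 45 minutes of daily home practice, but of different kinds: breathing awareness, body scanning and yoga in one arm, reading and resistance bands in the other. If people who stop are not measured, the group-by-time contrast sets those who stayed with MBSR against those who stayed with stress management education. The two sets need not be alike at baseline or in prognosis.

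This is a question of data collection, separate from which analysis set the SAP names. An intention-to-treat label cannot supply an outcome that was never measured. The sample-size paragraph speaks of a mixed-effect model. Such a model could keep people with a baseline only, but any information about their post value would then come from modelling assumptions.

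**Working it through.** **1. The plan's own retention figure.** Inputs: 20 analysed per group and 67% retention (SAP, sample size).
- 20 / (2/3) = 30 per group, 60 in total; 40/60 = 66.7%. Reproduced.
- The later target also reproduces: 24 / 0.80 = 30 (Attrition Considerations).

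So the plan tolerates up to 10 of 30 randomised participants per group missing from the comparison. That third covers class-stoppers, people who leave the study altogether and failed MSNA recordings. The documents do not split it.

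**2. Shift from comparing completers only.** Let C be the mean fall in MSNA among completers in an arm, G the amount by which stoppers' mean fall is smaller (taken as equal in both arms), and d the proportion stopping.
- All-randomised mean fall in an arm: C − d × G.
- All-randomised contrast: (C_MBSR − C_SME) − G × (d_MBSR − d_SME).
- Completer contrast: C_MBSR − C_SME.
- Difference between the two: G × (d_MBSR − d_SME).

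Assume G = 4 bursts/min, the size of the SAP's design effect:
- stopping differs by 10 points: 4 × 0.10 = 0.4 bursts/min, or 10% of the design effect;
- stopping differs by 20 points (for example 30% against 10%): 4 × 0.20 = 0.8 bursts/min, or 20%;
- equal stopping with an equal gap: 0.

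Equal stopping does not guarantee that the contrasts agree. If 20% stop in each arm and MBSR stoppers get none of a 4 bursts/min benefit, with no gap in the control arm, the all-randomised effect is 0.80 × 4 = 3.2, while completers show 4.0. These are two different target quantities. The gap is an error only if 4.0 is presented as the effect in everyone randomised.

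**3. What measuring stoppers would do to power.** The SAP gives neither an SD nor a pre-post correlation, so the stated power of about 0.89 cannot be reproduced directly. Solving back from 20 per group, a difference of 4 and two-sided alpha 0.05 (noncentral t; sidedness assumed) gives an SD of change of 3.87. Suppose all 30 per arm are measured, a proportion s stops, and stoppers keep a fraction f of the effect. The difference is then 4 × (1 − s) + 4 × f × s.

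| s | f | difference | power, 30 per arm |
|---|---|---|---|
| 20% | 0 | 3.20 | 0.88 |
| 20% | 0.5 | 3.60 | 0.94 |
| 20% | 1 | 4.00 | 0.98 |
| 33% | 0 | 2.67 | 0.75 |
| 33% | 0.5 | 3.33 | 0.91 |
| 33% | 1 | 4.00 | 0.98 |

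This treats every loss as a class-stopper who returns for testing and holds the SD constant, so it too is an illustration.

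**The case against.** A reader might infer that the plan restricts testing to completers, or that a site following it would have to turn a stopper away. The documents do not support that. In Specific Study Procedures the thing completed is the program, which may mean the group class. The study-duration section refers to all qualified participants and to the start and finish of the intervention, which can be read as the class calendar. Nothing makes the $50 session payment conditional on finishing the class. Only the overview uses wording about the individual, and it is a past-tense summary of timing. Consent forms and the proposal approved at the first institution are attached to the application but not shown; they may deal with withdrawal.

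A reader might also take the 20% or 33% as the share lost through this trigger. That does not follow: both may include people who left the study entirely, and the 33% also allows for failed recordings. The 19 participants at the first site who missed post-testing because of COVID-19 are a separate cause. The closure record for the second site gives eight enrolled and eight completed, so no class-stopping is visible there. The number of stoppers willing to be tested appears nowhere and could be small.

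All of this stands, and it limits the size of the point. It does not supply the missing visit. Two of the three timing statements refer to completion, the third needs interpretation, and the sample size is built on non-completers not contributing.

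**Conclusion.** The point holds as a gap in the visit schedule. The post-test is described as following completion, stopping the class is foreseen, and no outcome visit is provided for those who stop. In practice the ANOVA would then compare mainly completers. That is a consequence of the schedule and the sample-size allowance; the SAP does not state it as a rule.

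The amount of bias is unknown. The 0.4 to 0.8 bursts/min illustration rests on an assumed 4 bursts/min gap, equal in both arms, and an assumed 10 to 20 point difference in stopping. With a smaller gap or similar stopping rates it could be near zero. Exposure lies mainly among the 43 participants randomised at the first site, where stopping by arm is not reported. The change is worth making because the visit and its payment already exist in the plan.

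**What to change.** In Specific Study Procedures, schedule the post-test for every randomised participant willing to attend, within one stated window after the scheduled end of their class, whether or not they finished it. State that stopping the class is not withdrawal from testing. The overview gives one week and the study-duration section 10 days; these must be reconciled to a single window.

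The closure form records that participant follow-up has ended and analysis is complete, so the scheduling text can now serve only as a correction of the record or a template. For data already collected, report by arm how many were randomised, how many stopped the class and how many of those were post-tested. If stoppers were not tested, state in the SAP and with the results that the estimates apply to programme completers.

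The reporting needs only counts. Prospectively the cost is a few extra sessions of about 3 hours at $50 each, plus existing staff time. If 20% of 30 participants stopped and all returned, that is 6 × $50 = $300 in payments. The estimated effect may also be smaller once people who did not finish the class are included.
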